### 6.2 Settings

The cohorts for all study objectives will be drawn from a large EHR data source, representing a geographically diverse patient population. The data will include diagnoses, procedures, medications (prescribed and administered), clinical measures (biometric and laboratory values), and observations derived from clinical notes. A subset of the population will have linked, adjudicated claims data available to support sensitivity analyses.

EHR data, generated from routine clinical care offer timely clinical information not typically available in claims databases, including information on patient attributes, observations from physicians' notes, patient symptoms and history, diagnostic information, and planned and actual treatments, and prescription medicines not covered by health plans (e.g., CONTRAVE®). Notably, EHR data include measures of BMI for descriptive analysis and evaluation as a potential confounder and effect modifier. These EHR data will be linked to proprietary information from First Databank to identify medications of interest accurately, including NB.

### 6.3 Inclusion Criteria

For the main objective (1.0, 1.1), patients are eligible if they meet the following inclusion criteria:

- Have at least one prescription for NB between September 2014 and February 2020, including concurrent prescriptions (within 15 days) for naltrexone and bupropion; or have at least one prescription for lorcaserin;
- Have at least 180 days of data available prior to cohort entry with no evidence of prescriptions or dispensings of NB or lorcaserin;
- Have at least one BMI value available in the 180 days prior to cohort entry, inclusive of the index date;
- Have documentation of at least one outpatient medical visit 180 or more days prior to cohort entry, and at least one healthcare interaction in the 180 days prior to cohort entry;

- Are at least 18 years of age on the cohort entry date.

Of note, having at least one BMI value is the only inclusion criterion that is potentially missing within the EHR. Documentation of at least one outpatient medical visit more than 180 days prior to cohort entry, and at least one healthcare interaction in the 180 days prior to cohort entry is required. This criteria will facilitate the inclusion of individuals who appear to have sufficient engagement with an Arcadia-contributing health system and would have enough clinical data to meet the study objectives.

For the comparability study (2.0 and 2.1), inclusion criteria will be based on the CAMELLIA-TIMI 61 trial, insofar as the information is available in the data. Examples include:

- BMI  $\geq 27 \text{ kg/m}^2$ ;
- Age  $\geq 40$  years with history of documented myocardial infarction (MI) or ischemic stroke  $> 1$  month prior to baseline, peripheral artery disease, revascularization or significant unrevascularized coronary arterial stenosis;
- Women age  $\geq 55$  years or men age  $\geq 50$  years who have type 2 diabetes mellitus without established cardiovascular disease but at least one cardiovascular risk factor (hypertension, dyslipidemia, calculated creatinine clearance  $\geq 30$  to  $\leq 60 \text{ mL/min}$ , or urinary albumin-to-creatinine ratio  $\geq 30 \text{ } \mu\text{g/mg}$ ).

The full list of inclusion criteria are included in the CAMELLIA-TIMI 61 publication and protocol.

Where variables are not available in the EHR or claims data, we will search for suitable proxies based on the literature and the recommendations of a U.S.-licensed physician consultant.

For the case-crossover study (2.2), patients are eligible if they meet the following inclusion criteria:

- Experience a MACE event (“index event”) after September 2014;
- Have at least one prescription or dispensing of NB prior to the index event;
- Are at least 18 years of age at the time of the first prescription/dispensing of interest.

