## 2 DRUG DESCRIPTION

The product of interest is a fixed-dose combination of naltrexone hydrochloride (HCl), 8mg, and bupropion HCl, 90mg, for oral use via extended-release oral tablet. The product is marketed under the trade name CONTRAVE® in the United States (U.S.). It is a combination of an opioid antagonist (naltrexone) and an aminoketone antidepressant (bupropion). Each constituent active ingredient is available separately in various doses and formulations.

Following conventions within previous documents, hereafter we refer to the product CONTRAVE® as the branded product, under regulation. Use of CONTRAVE® or concomitant initiation of its constituent active ingredients, naltrexone and bupropion, will be referred to as NB within this protocol.

CONTRAVE® is indicated as an adjunct to a reduced-calorie diet and increased physical activity for chronic weight management in adults with an initial body mass index (BMI) of:

- 30 kg/m^2 or greater (obese) or
- 27 kg/m^2 or greater (overweight) in the presence of at least one weight-related comorbidity (e.g., hypertension, type 2 diabetes mellitus, or dyslipidemia).

CONTRAVE® is recommended to be initiated according to a dose-escalation schedule beginning with one tablet each morning in week one and increasing to up to two tablets twice daily beginning in week four.

The labeled contraindications include known allergy to any ingredient within CONTRAVE®; uncontrolled hypertension; seizure disorders; anorexia nervosa or bulimia; undergoing abrupt discontinuation of alcohol; use of benzodiazepines, barbiturates, or antiepileptic drugs; chronic opioid use; and taking currently, or within the past 14 days, a monoamine oxidase inhibitor.

As specified in the product labeling under Warnings and Precautions and Limitations of Use, the effect of CONTRAVE® on cardiovascular morbidity and mortality has not been established. Additionally, the safety and effectiveness of CONTRAVE® in combination with other products intended for weight loss, including prescription drugs, over-the-counter drugs, and herbal preparations, have not been established. In this protocol, we propose to evaluate the potential effects of NB on cardiovascular endpoints.

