	
Inclusion and exclusion criteria for the main objective will ensure that only new users are included, and that the NB and comparison groups are comparable on risk factors for MACE after application of propensity score (PS) matching weights.
 
Inclusion and exclusion criteria for the additional objectives will align with those used in the 2018 trial assessing cardiovascular endpoints among lorcaserin users, insofar as the data support a comparable replication.
		
Variables:	
The key variables are initiation of NB, initiation of lorcaserin (active comparator), time on treatment, and the endpoint of MACE. The individual components of MACE will also be quantified. Covariates will be derived from clinical measurements, past medical history, diagnoses, observations, and prescription records. Multiple imputation will be applied to address missing data, coupled with PS analyses to address confounding.
		
Data Sources:	
EHR and linked claims data from Arcadia Data Research. The data currently cover approximately 75 million people in the U.S.
		
Study Size:	
There are approximately 37,000 apparent NB initiators in the Arcadia data.
 
There are approximately 16,000 apparent lorcaserin initiators.
		
Data Analysis:	
Descriptive statistics of the study cohorts, multiple imputation of missing covariates, estimation of crude incidence rates of MACE among initiators of NB, and adjusted incidence rates of MACE after applying PS matching weights will be calculated (1.0 and 1.1). Analogs to intention-to-treat and per-protocol cohort analyses will be conducted. The analysis will also follow the principles of the RCT DUPLICATE Initiative (2.0 and 2.1) to assess the concordance between findings in an EHR study to those in the lorcaserin cardiovascular safety endpoints trial. In addition, we will conduct a case-crossover study to assess the effects of NB on MACE (2.2) and other sensitivity analyses.
		
Milestones:	
 
 Start of Data Collection End of Data Collection	September 2014 February 2020	
 
	Start of Data Collection End of Data Collection	September 2014 February 2020
Start of Data Collection End of Data Collection	September 2014 February 2020		

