## 6 RESEARCH METHODS

### 6.1 Study Design

A retrospective cohort study design will be used for the main objective and endpoints. Initiators of NB will be identified between September 2014 and February 2020. Contemporaneously, we will identify all lorcaserin users between 2012 and 2020. A self-controlled, case-crossover design will be used for the sensitivity analysis (2.2).

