## 6.4 Exclusion Criteria

For the main objective, patients are not eligible if they have a diagnosis of any of the following conditions in the 180 days before the cohort entry date:

- Epilepsy;
- Bulimia;
- Anorexia nervosa;
- Surgical procedure for weight loss.

Patients also must not have been prescribed opioids or monoamine oxidase inhibitors in the 180 days before entry into the cohort.

Patients with prescriptions for both NB and lorcaserin will be randomly assigned to a baseline treatment group to preserve sample size and mitigate selection bias.

Patients are not eligible for inclusion in the comparability study if they have any of the following, as feasibly measured in the Arcadia data, including:

- Congestive cardiac failure;
- Known left ventricular ejection fraction <20%;
- Moderate or higher pulmonary hypertension ;
- Known severe valvular disease;
- Moderate renal impairment, severe renal impairment, or end-stage renal disease;
- Severe hepatic impairment;
- Use of other products intended for weight loss;
- Use of, within 1 month prior to baseline, more than one other serotonergic drug including, but not limited to:
  - Selective serotonin reuptake inhibitors;
  - Serotonin norepinephrine reuptake inhibitors;
  - Tricyclic antidepressants;
  - Bupropion;
  - Triptans;
  - St. John's Wort and tryptophan;
  - Monoamine oxidase inhibitors, linezolid, dextromethorphan, lithium;
  - Tramadol, antipsychotics or other dopamine antagonists;
- Use of drugs known to increase the risk for cardiac valvulopathy within 6 months prior to baseline including, but not limited to:
  - Cyproheptadine;
  - Amoxapine;
  - TCAs;
  - Mirtazapine;
  - Pergolide;
  - Ergotamine;

- Methysergide;
- Cabergoline;
- History or evidence of clinically significant disease (e.g., malignancy, cardiac, respiratory, gastrointestinal, renal or psychiatric disease);
- Use of lorcaserin HCl within 6 months prior to screening;
- Hypersensitivity to lorcaserin HCl or any of the excipients.

The full list of exclusion criteria are included in the CAMELLIA-TIMI 61 publication and protocol.

[figure not shown]
Similar to the exclusion criteria for the primary objective, patients with any of the diagnoses or prescriptions for opioids and/or monoamine oxidase inhibitors in the 180 days prior to the index event date will be excluded from the case-crossover analysis.

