## 6.5 Variables

### 6.5.1 Exposure

Initiation of NB and lorcaserin will be identified using Hierarchical Ingredient Code Lists (HICLs) from First Databank. If necessary, individual searches of National Drug Codes (NDCs) and free-text strings will also be used. See **Figure 1** for visual depiction of the study design.

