**Figure 1. NB safety study design**

[figure not shown]

For the cohort, among the subset of patients with EHR data whose records can be linked to health insurance claims, we will assess the concordance between receiving a prescription for NB and lorcaserin (in the EHR) and filling the prescription (in the claims).

The time of entry into the NB cohort will be the date of first prescription for those taking CONTRAVE®, the date of the second overlapping prescription of naltrexone or bupropion in the case of concomitant use of naltrexone and bupropion, or the date of first prescription for lorcaserin from date of approval in the U.S. to withdrawal from the market, as applicable.

In the case-crossover study, a 90-day hazard window will immediately precede the index event date within which the occurrence of a prescription or dispensing will define exposure status. Similarly, a 90-day referent window will precede the hazard window, with exposure status designated comparably. A 30-day washout window between the hazard and referent windows will be used to mitigate any carryover effects from the prior exposure. Please see **Figure 2** for a visual depiction of the case-crossover study design.

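### The component-route entry rule does not enforce the protocol's own new-user definition: a continuing user of naltrexone or bupropion alone can enter the pooled NB cohort on adding the other drug

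*Combined protocol and SAP*

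**What the plan says.** - **Definition (Section 2):** "Use of CONTRAVE® or concomitant initiation of its constituent active ingredients, naltrexone and bupropion, will be referred to as NB". This is the only place where NB is defined.
- **New-user statement (Section 3, Population):** the main-objective criteria "will ensure that only new users are included".
- **Description of exposure:** Section 6.1 states "Initiators of NB will be identified between September 2014 and February 2020" and Section 6.5.1 states "Initiation of NB and lorcaserin will be identified using Hierarchical Ingredient Code Lists". Both speak of initiation, but neither defines NB.
- **Eligibility (Section 6.3):** at least one NB prescription in the accrual period, "including concurrent prescriptions (within 15 days) for naltrexone and bupropion", with at least 180 days of prior data showing "no evidence of prescriptions or dispensings of NB or lorcaserin".
- **Day 0 (Section 6.5.1, text below Figure 1):** for separate ingredients, "the date of the second overlapping prescription of naltrexone or bupropion in the case of concomitant use of naltrexone and bupropion".
- **Drug exclusions for the main objective (Section 6.4):** "Patients also must not have been prescribed opioids or monoamine oxidase inhibitors in the 180 days before entry into the cohort". Bupropion appears in 6.4 only among the serotonergic drugs of the comparability study.
- **Covariates (Section 6.5.3):** neither bupropion nor naltrexone is listed, though the medication list is introduced in a way that may not be exhaustive.
- **Analysis (Section 9.5.3):** the overall NB cohort is analysed, and results are also stratified into CONTRAVE initiators and concomitant users of the two ingredients.

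**The concern.** A new-user design aligns the start of exposure, the start of follow-up and the measurement of baseline covariates. For a patient who adds naltrexone to established bupropion, or the reverse, only one ingredient starts at day 0. Any event on the first ingredient falls before follow-up, and baseline blood pressure, heart rate and BMI may already reflect that drug. Section 9.5.1 interprets the intention-to-treat result as the effect of starting treatment. The pooled primary estimate could mix patients who start both drugs together with patients already exposed to one.

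There is also a reproducibility problem. A programmer working from Section 2 and one working from Section 6.3 could build different primary cohorts from the same data.

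**Working it through.** **Step 1. Run a constructed patient through the rules.** A long-term bupropion user has a renewal on day −10 and a first naltrexone prescription on day 0.

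| Rule | Result |
|---|---|
| 6.3, both drugs prescribed within 15 days | Met (10 days apart) |
| 6.3, 180 days without NB or lorcaserin | Met: bupropion alone is not NB under Section 2 |
| 6.5.1, day 0 is the second overlapping prescription | Met on the naltrexone date |
| 6.4, no opioid or MAOI in 180 days | Not triggered by bupropion |
| Section 2, the two ingredients initiated together | **Not met** |

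The remaining criteria (age, BMI value, visits, excluded diagnoses) do not concern prior use of either ingredient. The patient enters under 6.3 and 6.5.1 but is not NB under Section 2. Under 6.3, entry does require a prescription of the existing drug within 15 days of the added one, so not every add-on user enters.

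**Step 2. Could the washout be read as covering single ingredients?** Day 0 is the second prescription of the pair. Unless both are written on the same day, the first falls inside the 180 days and would breach such a washout. That reading would exclude every staggered pair that 6.5.1 admits.

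**Step 3. Do the strata solve it?** They isolate CONTRAVE initiators. The overall estimate still pools both routes, and the component stratum does not separate simultaneous starters from add-on users.

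**Step 4. Possible size (all inputs assumed).** If add-on patients are a share s of weighted NB person-time and their MACE rate is k times that of other NB patients, the pooled NB rate is multiplied by 1 + s(k − 1).
- s = 0.05: 1 + 0.05(−0.3) = 0.985 at k = 0.7; 1 + 0.05(0.5) = 1.025 at k = 1.5.
- s = 0.20: 1 + 0.20(−0.3) = 0.94 at k = 0.7; 1 + 0.20(0.5) = 1.10 at k = 1.5.

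**Step 5. The plan's power figure and the cost of excluding.** Inputs: 37,000 NB and 16,000 lorcaserin initiators (Abstract), 2 MACE per 1,000 person-years and relative risk 2.0 (Section 8.2). Assumed: two-sided alpha 0.05, mean follow-up, and no loss from weighting. Follow-up and alpha are not in the readable text, and Figure 3 is not shown.

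Power = Φ[(p1 − p0 − 1.96·s0)/s1], where s0 = √{p̄(1 − p̄)(1/n1 + 1/n0)} and s1 = √{p1(1 − p1)/n1 + p0(1 − p0)/n0}.

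At one year, p0 = 0.002, p1 = 0.004 and p̄ = (148 + 32)/53,000 = 0.003396. Then s0 = 0.0005505, s1 = 0.0004821 and (0.002 − 0.001079)/0.0004821 = 1.91, giving 97.2%. At six months the result is 75.6%. The stated power above 80% is consistent with one year of follow-up but cannot be reproduced strictly.

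| Scenario | One year | Six months |
|---|---|---|
| As planned | 97.2% | 75.6% |
| NB arm −10% (33,300) | 96.7% | 74.4% |
| NB arm −20% (29,600) | 96.1% | 72.9% |
| NB arm −30% (25,900) | 95.2% | 71.1% |
| Both arms −10% | 95.5% | 70.6% |
| Both arms −30% | 89.1% | 58.5% |

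A Wald test on the log rate ratio gives lower levels but a similar cost for 30% NB loss: 94.5% to 92.9% at one year, 71.0% to 67.8% at six months.

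The counts are apparent initiators, before the BMI, visit and opioid criteria are applied. At 16,000 per arm (1:1) one-year power is 90.5%; if an assumed 75% were eligible (12,000 per arm) it is 80.9%.

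**The case against.** The strongest reply is that the text can be harmonised. Section 2's definition governs the whole protocol, so NB in Section 6.3 inherits joint initiation and the 15 days is merely the timing window. The protocol also uses its terms loosely: Section 6.1 speaks of lorcaserin users in the sentence after NB initiators. Figure 1 is not shown and may carry an ingredient-level washout. This reading is possible, but Section 6.3 spells out its own test without requiring a first prescription, and Sections 6.5.1 and 9.5.3 both speak of concomitant use. At the least, the readable text permits two cohorts.

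Two further points stand in part. The CONTRAVE stratum is free of the component route, and the baseline list (prior MI and stroke, blood pressure, heart rate, mood disorders) captures some of the indication and history, though not exposure to the ingredient. The pre-exposure argument also applies to a CONTRAVE starter already taking bupropion. A reader might infer that such patients breach the new-user rule as well. The documents do not support that: Section 2 counts use of the branded product as NB, so these patients are new users of NB as defined. For them the issue is unlisted adjustment, which is why the fix treats them by covariate and sensitivity analysis.

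**Conclusion.** The concern holds as a gap between the stated new-user definition and the operative entry rule for the component route. It affects the pooled primary cohort and should be corrected before analysis.

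A reader might go further and infer that the primary estimate is materially biased, or biased towards no difference. The documents do not support either. They give no count of component-route entrants or of prior single-ingredient users, and nothing fixes the direction. Under the assumed inputs the NB rate shifts by a factor of 0.94 to 1.10 at a 20% share, small beside a relative risk of 2.0. Nor should every add-on user be assumed to enter, given the 15-day condition.

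The power figures show that excluding add-on users costs little under the stated assumptions. They do not show that the study is adequately powered, and 16,000 per arm should not be taken as a lower bound.

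**What to change.** (a) Reconcile Sections 6.3 and 6.5.1 with Section 2. For component-route entrants, require no prescription or dispensing of naltrexone alone or bupropion alone in the 180 days before the first prescription of the qualifying pair. Counting back from that prescription stops the pair from excluding itself. With the 15-day window governing, up to 180 + 15 = 195 days of data before day 0 are needed. Pre-specify a sensitivity analysis that keeps add-on users.

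(b) Add prior single-ingredient bupropion or naltrexone use to the propensity-score covariates (Sections 6.5.3 and 9.4) for all patients. Measure it over the 180 days before entry for CONTRAVE and lorcaserin starters, and over the 180 days before the first prescription of the pair for component-route entrants, so that the pair is never counted as prior use. Pre-specify a sensitivity analysis excluding prior single-ingredient users from both arms, since CONTRAVE starters already on an ingredient stay in the primary analysis.

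(c) Report component-route counts and prior single-ingredient use by arm before outcomes are tabulated.

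The cost is wording and query changes in data already held, some NB patients lost, and a primary estimate that no longer covers add-on users. A 30% loss of the NB arm costs about 2 points of power at one year (97.2 − 95.2) and 4.5 at six months (75.6 − 71.1). The two-arm exclusion costs more, which is why it is kept as a sensitivity analysis. Actual losses are unknown until (c) is done.

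### The case-crossover windows reach back 210 days, but the plan requires no recorded history before the index event and screens exclusions over only 180 days, so an unrecorded referent window can be coded as unexposed

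*Combined protocol and SAP*

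**What the plan says.** Section 6.5.1 defines the windows. It states that "a 90-day hazard window will immediately precede the index event date", and that exposure depends on whether a prescription or dispensing occurs in that window. It adds that "a 90-day referent window will precede the hazard window, with exposure status designated comparably". The gap is also specified: "A 30-day washout window between the hazard and referent windows will be used to mitigate any carryover effects".

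Section 6.3 lists three case-crossover inclusion criteria: a MACE after September 2014, age 18 or over, and this one on exposure: "Have at least one prescription or dispensing of NB prior to the index event". None of them concerns length of record, enrolment or healthcare contact. The same section does set a history rule for the main objective (1.0, 1.1), "Have at least 180 days of data available prior to cohort entry", together with an outpatient visit 180 or more days before cohort entry. Those rules are anchored on cohort entry and are not carried over to the case-crossover study.

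Section 6.4 applies the diagnosis, opioid and monoamine oxidase inhibitor exclusions to the case-crossover study over a fixed look-back: patients meeting them "in the 180 days prior to the index event date will be excluded from the case-crossover analysis".

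Section 9.5.3 analyses the pairs by conditional logistic regression. Section 10.2 says the case-crossover results will help show how far residual confounding may affect the cohort analysis.

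**The concern.** A case-crossover comparison is fair only if exposure is ascertained equally well in both windows. When a record is short, the earliest days are lost first, and here those are referent days. The occurrence rule has no category for unknown, so a window with no record is read as a window with no drug.

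Take a patient who has used NB continuously for a year and whose record begins 100 days before the event. The whole hazard window is seen and coded exposed. The whole referent window precedes the record and is coded unexposed. The true pair is concordant and should contribute nothing; the coded pair counts as evidence that NB precedes MACE. Conditional logistic regression uses only discordant pairs, so errors of this kind enter the estimate directly.

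At stake is the reading of a supporting analysis. An inflated odds ratio could look like a safety signal, or could lead the sponsor to misjudge the residual confounding in the cohort comparison.

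**Working it through.** **Span of the windows** (Section 6.5.1). Counting back from the event, the hazard window is days 1–90, the washout days 91–120 and the referent window days 121–210. Total: 90 + 30 + 90 = 210 days.

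**Recorded history required** (Section 6.3, case-crossover criteria): none stated, against 210 days needed. The plan gives no look-back total, sample size or power for this analysis, so there is no figure of its own to reproduce.

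**Exclusion look-back** (Section 6.4): 180 days. This covers the hazard window, the washout and referent days 121–180. Referent days left unscreened: 210 − 180 = 30, which is 30/90 = 33% of that window.

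**Direction of the bias.** Let π11 be the share of cases truly exposed in both windows, and π10 and π01 the hazard-only and referent-only shares. Suppose a share u of cases, unrelated to exposure, has an unseen referent window coded as unexposed. Then:

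- hazard-only pairs = π10 + u·π11
- referent-only pairs = (1 − u)·π01

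If the true odds ratio is 1, then π10 = π01 and

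OR = (1 + u·π11/π10) / (1 − u).

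This exceeds 1 for any u above 0. It rises with π11/π10, that is, with how persistently patients use the drug.

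**Illustrative size.** With independent windows of exposure prevalence p, π11/π10 = p/(1 − p). Both u and p are assumptions.

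| u | p = 0.1 | p = 0.3 |
|---|---|---|
| 5% | 1.06 | 1.08 |
| 10% | 1.12 | 1.16 |
| 20% | 1.28 | 1.36 |

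Worked cell, u = 10% and p = 0.1: (1 + 0.1 × 0.1/0.9)/0.9 = 1.0111/0.9 = 1.12.

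If only the earliest 30 referent days are unseen in a share u of cases, and prescriptions are rare, OR ≈ 1/(1 − u/3). At u = 10% that is 1/0.967 = 1.03.

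**Comparing remedies.** A second null model assumes exponential persistence (mean 180 days), exponential time to event (mean 2 years = 730 days) and a window exposed if the patient is on drug at any time in it. Already-treated patients' records begin part-way through treatment; new users have a full earlier record.

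| Share already treated when record begins | Coded as the plan states | Referent windows observed | 210 days of record before the event required |
|---|---|---|---|
| 0% | 1.42 | 1.42 | 1.42 |
| 10% | 1.42 | 1.32 | 1.32 |
| 25% | 1.42 | 1.16 | 1.16 |

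At 10% and 25%, a history rule anchored on the index event restores the value that observed windows would give. Restricting instead to patients with 210 NB-free days before their first NB prescription leaves 1.42.

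**The case against.** The strongest objection concerns size. In the second model the coded odds ratio is 1.42 even when nobody is already treated at the start of the record. A reader might infer that unseen referent windows inflate a null odds ratio to about 1.4 and that a history rule would bring it back to 1. Neither is supported. The 1.42 among pure new users is exposure-trend bias: events soon after starting have a referent window before NB began. That needs its own correction. The observed-window values are not unbiased benchmarks either. At a 50% already-treated share the value is 0.90, because the stopping trend in already-treated patients then outweighs the starting trend in new users. Only the gap between the coded and observed columns belongs to this point, and it depends on assumed shares, persistence and follow-up. This part of the objection stands.

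A reader might also infer that the analysis should be confined to new users. The defect concerns the 210 days before the event, not the time before first use. A patient whose record starts on day 0, who starts NB on day 100 and has an event on day 500 has both windows fully seen, yet a rule of 210 NB-free days before first use would drop that patient.

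Nor does the screening gap share the upward bias. The exclusion removes a person from both windows, and leaving days 181–210 unscreened does not hide any NB prescription. No direction follows.

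Finally, this is one sensitivity analysis, not the primary MACE comparison. Section 10.1 already concedes under-capture from non-contributing providers, and Figure 2 is not available in the text reviewed. Those points limit the weight of the concern. They do not answer it: the general caveat sets no observability rule, and the text places the washout between the two 90-day windows, so the total is not 180 days.

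**Conclusion.** The point holds as a gap in the case-crossover specification. As written, the criteria admit cases whose referent window is wholly or partly unrecorded, and the exposure rule would count that time as unexposed. The resulting bias is upward relative to correctly observed windows. Its size cannot be derived, because the documents give neither the distribution of record lengths among cases nor the persistence of NB use; the figures above are illustrations.

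The conclusion rests on two readings: that the occurrence rule is applied literally where there is no record, and that case-crossover patients need not belong to the main cohort. If membership were required, 180 days before entry would cover the windows for events 30 or more days after entry (180 + 30 = 210), but Section 6.3 does not say so. Without a history rule the hazard window is not guaranteed complete either; it is simply the last to be lost.

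The 180-day screen is a secondary consistency point. The primary cohort analysis is not directly affected, but Section 10.2 uses this analysis to judge residual confounding there, so the gap should be closed before the analysis is run.

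**What to change.** 1. In the case-crossover criteria of Section 6.3, require at least 210 days of recorded, observable history before the index event, and state how observability is established (for example, by data-availability and visit criteria of the kind already used for the main objective, re-anchored on the index event).
2. In Section 6.4, extend the case-crossover look-back for the exclusion diagnoses, opioids and monoamine oxidase inhibitors from 180 to 210 days before the index event, so that both windows are screened alike.

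The cost is two text changes and the loss of cases with short records or with an excluding record in days 181–210. The documents do not give that number, so the report should state how many cases each rule removes. These changes do not deal with exposure-trend bias, which has to be handled separately.
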